The following table summarizes the criteria for selecting patients from the AF population in the SNDS data.

Cohort	Inclusion criteria	Exclusion criteria
AF Population	
 o Identified patients with AF aged 18 years and older at diagnosis of AF 	
 o - Beneficiaries who are insufficiently identifiable or for whom there are technical

		
constraints in SNDS [fictive pseudoNIR (patient identifier), twins];
 
 ○ - Beneficiaries affiliated to a settlement institution from the oversea French department Mayotte; ○ History of valvular pathology and contraindications to OAC treatment.
--	--	---

Note: Other exclusion criteria will be discussed together with the Scientific Committee

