9.2.1.1 Inclusion period

Within the extraction period, the inclusion period is from January 1st, 2016 to December 31st, 2019 and to December 31st, 2020 for sensitivity analyses.

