9.2.1.3 Historical period

The historical period is a period of 2 years before the index date in order to distinguish incident and prevalent AF-patients, describe patient's comorbidities, medical history and history of treatments. Consequently, this historical period starts from January 1st, 2014.

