9.2.1.4 Follow-up and Censoring

[figure not shown]
The Follow-up period starts at index date and ends on the date of occurrence of one of the following events:

- Death;
- End date of the study fixed to December 31st, 2019 or to December 31st, 2020 for sensitivity analyses;

- Date of the last reimbursement of care recorded in the SNDS (patients with no consumption or reimbursement of care in the 12 months following the date of last consumption).

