Then, a logistic model included 14 independent covariables will be applied on unclassified patients to identify AF outpatients. The model will include following covariables: age, gender, use of treatments as use of beta-blockers, antiarrhythmics, antihypertensive drug, holter/echocardiography procedures, cardiologist prescriber, D-dimer blood test reimbursement and presence of hospitalization for arterial thromboembolic event.

Finally, for each unclassified patient, those with a predicted probability above the cut-off value providing specificity of 95% (sensitivity: 63%), will be assumed to be AF outpatients.

9.2.3.2 *Exclusion Criteria*

Patients will be excluded from the study if they meet any exclusion criteria:

- Patients with at least one hospital stay with an ICD-10 code in PD, RD or AD for associated valve disease, ICD-10 codes I05 to I09, I34 and I39, or valve surgery;
- Standard SNDS exclusion criteria (e.g. unicity of identifier not guaranteed, twins, aberrant demographic data, beneficiaries from Mayotte overseas French territory).

[figure not shown]

Figure 2. AF study population according to inclusion and non-inclusion criteria

9.2.3.3 *Populations*

Two populations of AF patients will be considered for analyses according to study objectives:

9.2.3.3.1 *Prevalent AF population*

Prevalent AF patients will be defined as patients diagnosed with AF during the historical period.

Prevalent AF population will be considered for the following analysis:

- To estimate the annual prevalence of patients with non-valvular AF, exposed and unexposed to OAC (objective 4).

9.2.3.3.2 *Incident AF population*

Incident AF patients will be defined as patients newly diagnosed with AF (i.e. no AF diagnostic during the historical period) from January 1st, 2016 to December 31st, 2019 (inclusion period), and to December 31st (2020 for sensitivity analyses).

For incident AF population, two datasets of incident AF patients will be considered for the following analyses:

- For longitudinal analyses: objectives 1, 2, 3 and 7 (cf. 8. Objectives)

Inclusion of patients with:

- An AF newly diagnosed during inclusion period

AND

- No reported events of interest (stroke, major bleeding, and death) within 30 days before index date (i.e. for patients for whom the date of inclusion is not the date of the first dispensation of OA) (cf. 9.2.3.1. Inclusion Criteria)

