D-dimer blood test	
Binary variable (Yes / No)
 
Equals to “Yes” if the patient has reimbursements for at least one D-dimer blood test during the 6 weeks preceding the first date of OAC delivery

	
NABM codes: 1021, 1022.
 
Equals to "No" in other cases

Hospitalization for arterial thromboembolic event	
Binary variable (Yes / No)
 
Equals to "Yes" if the patient is hospitalized at least once with any discharge diagnosis (i.e., principal, related or associated diagnosis) of arterial thromboembolic event (ischemic stroke or transient ischemic attack or systemic arterial embolism) during the 6 weeks preceding the first date of OAC delivery
 
ICD-10 codes: I63 (ischemic stroke) except I63.6 (cerebral infarction due to cerebral venous thrombosis, non-pyogenic), G45 (transient ischemic attack), I74, N28, D73.5, K76.3 (systemic arterial embolism).
 
Equals to "No" in other cases

Then, all the variables representing the exclusion criteria will be derived for each AF patients included after the inclusion criteria and the application of the algorithm ([Table IV](#)).

Table IV. Derived variable for the selection of the population – Exclusion criteria

Variable	Definition
Valvular pathology	
Binary variable (Yes/No)
 
Equals to "Yes" if the patient is hospitalized at least once with any discharge diagnosis (i.e., principal, related or associated diagnosis) of valve disease or valve surgery, during historical or inclusion period
 
ICD-10 codes: I05.x, I06.x, I07.x, I08.x, I09.x, I34.x, I39.x
 
CCAM codes (valve surgery): DBAF003, DBAF002, DBAF005, DBAF004, DBAF001, DBPA002, DBPA004, DBPA005, DBPA006, DBPA007, DBMA008, DBMA012, DBMA003, DBMA002, DBMA011, DBKA004, DBKA008, DBKA007, DBKA012, DBKA010, DBKA005, DBKA002, DBKA006, DBKA003, DBKA001, DBKA011, DBKA009, DBMA007, DBMA013, DBMA005, DBMA009, DBMA010, DBMA006, DBMA001, DBMA015, DBMA004, DBLF009, DBLF001, DBLA004, DBBF198, DBSF001, DBEA001.
 
Equals to "No" in other cases

Standard SNDS exclusion criteria	
Binary variable (Yes / No)
 
See Data Management Plan in section Error! Reference source not found.

Moreover, all the variables used to define the sub-populations will be derived for each patient selected in the study population ([Table V](#)).

Table V. Derived variables for the selection of the populations – Sub-populations

Variable	Definition

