9.7.3 Planned Analysis for the Primary Objective

9.7.3.1 To estimate the incidence rate of stroke (ischemic or hemorrhagic), major bleeding and death in AF patients exposed to OAC (VKA or DOAC) and unexposed to OAC

The analysis of incidence rate for the first occurrence of each event of interest (stroke, major bleeding and death) will be conducted in the population of AF incident patients excluding those with a reported outcomes of interest up to 30 days prior index date.

As a reminder, incident AF patients will be the patients newly diagnosed AF during the inclusion period i.e., with a date of first diagnosis of AF, identified by the date of the start of LTD or of the index hospital stay during inclusion period, or the date of initiation of the OAC.

Event rates will be estimated over the 4-year period 2016-2019, in the overall population and according to the treatment exposure.

The incidence rate for each event of interest (stroke, major bleeding and death) will be defined as the number of events occurring during the follow-up period divided by the number of person-years of follow-up (sum of durations of follow-up period for incident patients).

Incidence rates in unexposed patients will be standardized by age using exposed patients as the population of reference.

Analyses will be descriptive in nature (proportion and 95% confidence interval).

Event rates will also be displayed by sub-populations (see section [9.2.3.4](#)).

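### The valve-disease exclusion in SAP Table IV uses codes recorded after the index date, so cohort entry depends on the future and the event rates can be biased in a direction the documents do not settle

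*SAP*

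**What the plan says.** - **Exclusion flag.** SAP 9.4.1, Table IV sets valvular pathology to Yes for any discharge diagnosis "of valve disease or valve surgery, during historical or inclusion period". The window is not tied to the index date.
- **Inclusion period.** SAP 9.2.1.1: "the inclusion period is from January 1st, 2016 to December 31st, 2019", extended to the end of 2020 for sensitivity analyses.
- **Historical period.** SAP 9.2.1.3: "The historical period is a period of 2 years before the index date".
- **Follow-up.** SAP 9.2.1.4: "The Follow-up period starts at index date and ends on the date of occurrence of one of the following events". One of these events is the "End date of the study fixed to December 31st, 2019 or to December 31st, 2020 for sensitivity analyses".
- **Primary measure.** SAP 9.7.3: number of events "divided by the number of person-years of follow-up (sum of durations of follow-up period for incident patients").
- **Other statements of the exclusion.** SAP 9.2.3.2 says "Patients with at least one hospital stay with an ICD-10 code in PD, RD or AD for associated valve disease" and gives no window. The criteria text of Protocol 3.2.1 gives none either. Only the Protocol's summary selection table uses the word history: "History of valvular pathology and contraindications to OAC treatment".

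SAP Table V looks for coronary disease and previous stroke at the index date and in the 2 years before it. None of the sensitivity analyses in SAP 9.7.6 varies the valve window, and neither limitations section mentions it.

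**The concern.** Eligibility for a cohort followed from an index date should be decidable on that date. Under Table IV it is not. A code recorded during follow-up deletes the patient back to index, including all time and events before the code. A patient who dies in 2016 cannot acquire a 2018 code and stays in; a comparable survivor can be removed. The exposure to removal also depends on entry date, from almost 4 years for the first entrants to 0 days for the last.

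The cohort defined this way feeds both the primary incidence rates (SAP 9.7.3) and the Cox models (SAP 9.7.4.2). Read literally, the 2020 sensitivity analysis makes it worse: a longer inclusion period lengthens the exclusion window, so patients kept in the main cohort could drop out on a 2020 code. That analysis would then change the cohort as well as the calendar period.

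**Working it through.** The plan states no figure to reproduce. The first step is date logic; the rest is illustration.

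**1. Dates.** The window for a disqualifying code closes on 31 December 2019 (SAP 9.2.1.1), and so does follow-up (SAP 9.2.1.4). Every day of follow-up in the main analysis is therefore a day on which a code can remove the patient. No other section limits the flag to time before index.

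**2. Death, with valve coding independent of death.** All rates here are assumptions: death d = 0.10 per year, valve coding v per year, entry uniform over T = 4 years, λ = d + v.

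- Mean time to the first of death, code or end of study: A = [1 − (1 − e^(−λT))/(λT)]/λ
- Mean person-time of patients who reach the end neither dead nor coded: B = [1 − e^(−λT)(1 + λT)]/(λ²T)
- Share removed = vA
- Deaths retained = dA
- Person-years retained = (d/λ)A + (v/λ)B

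For v = 0.05: λ = 0.15, A = 1.6535, B = 1.3545. Share removed = 0.05 × 1.6535 = 8.3%. Deaths per patient = 0.1653. Person-years per patient = 0.6667 × 1.6535 + 0.3333 × 1.3545 = 1.5538. Rate = 0.1653/1.5538 = 0.1064, against a true 0.1000.

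| v per year | Removed | Death rate under Table IV | Overstatement |
|---|---|---|---|
| 0.01 | 1.7% | 0.1013 | 1.3% |
| 0.02 | 3.4% | 0.1025 | 2.5% |
| 0.05 | 8.3% | 0.1064 | 6.4% |
| 0.10 | 15.6% | 0.1132 | 13.2% |

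Excluding only on codes up to index and censoring at a later code gives dA/A = d, the true rate. At v = 0.02 the overstatement is about 3.4% for first-year entrants and 0.7% for last-year entrants.

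**3. Death, with higher mortality after a valve code.** Simulation of 4 million patients, with the death rate multiplied from the code date onward:

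| Multiplier | Comparator | v = 0.02 | v = 0.05 | v = 0.10 |
|---|---|---|---|---|
| 2 | full follow-up | about +0.3% | +0.9% | +2.5% |
| 3 | full follow-up | −1.5% | about −3.3% | −5.1% |
| 2 or 3 | censored at the code | +2.5% | +6.4% | about +13.2% |

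The sign depends on the link between valve coding and death, and on the estimand used as comparator.

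**4. Stroke.** Assumed stroke rate 0.02 per year, death 0.10, v from 0.01 to 0.05. If coding is independent of stroke, the ratio of the Table IV rate to the full-cohort rate is 1.00. If 5%, 10% or 20% of stroke stays also carry a valve code, it is about 0.95, 0.90 or 0.80. Such overlap is possible because SAP Tables IV and VIII both accept discharge codes in any position. Bleeding was not simulated; the same mechanism applies.

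**5. Hazard ratio.** With equal valve coding in both groups and a true death-rate ratio of 1.5, the look-ahead changes the ratio by less than 0.5% even at v = 0.10.

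**The case against.** **Later codes may reveal old disease.** The study targets non-valvular AF, and the flag relies on hospital diagnoses and procedures with a 2-year lookback. A valve code after index can be the first record of disease already present, so some of the patients removed are rightly excluded. This stands in part: the removed shares above cannot all be read as wrongful removals. It does not cure the look-ahead. Patients with unrecognised disease who die early stay in while survivors with the same disease leave, and the SAP does not offer this rationale.

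**The Protocol does not clearly say otherwise.** The full criterion in Protocol 3.2.1 has no window, and history appears only in the summary table. Protocol 3.2.1 also says the exclusions follow two earlier studies, but it reports no window from them. A reader might infer a plain SAP–Protocol contradiction; under-specification in the Protocol is the fairer description.

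**AF inclusion also spans the historical and inclusion periods.** True, but for incident patients follow-up starts no earlier than the first evidence of AF (SAP 9.2.1.2). That criterion does not look past index; the valve flag does.

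**The bias is assumed.** This stands as to size and direction. Every rate in the working is an assumption, and at 1% to 2% coding per year the effect on death is only about 1.3% to 2.5% even when coding is independent of death.

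**Conclusion.** Wrong as written. Table IV makes cohort membership depend on information recorded after index, and nothing else in either document limits it. That conclusion rests on the SAP's dates alone.

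The consequence is that the primary rates can be biased, by an amount the documents do not allow anyone to compute. The illustrated 1.3% to 13.2% overstatement of the death rate requires 10% mortality, uniform entry, coding at 1% to 10% per year and independence of coding from death.

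Three stronger readings are tempting and not supported:

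- **All primary rates are overstated.** Against full follow-up the death bias can vanish or reverse if valve-coded patients die more often. Stroke shows no bias under independence, and is understated if stroke stays also carry valve codes.
- **The hazard ratios are biased.** The Cox models use the affected cohort, but a material effect on the ratios would need valve coding that differs by exposure group. That is plausible, and nothing in the documents shows it.
- **Every patient removed on a later code was removed wrongly.** Some may have had valve disease at index.

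**What to change.** 1. In SAP Table IV, restrict the valve diagnosis and valve surgery flag to the index date and the 2 years before it, the window Table V already uses for coronary disease and previous stroke.
2. Put the same window into SAP 9.2.3.2 and into both the criteria text and the selection table of Protocol 3.2.1.
3. To keep the target population non-valvular, censor follow-up at the first post-index valve code in the main analysis. Report follow-up without that censoring as a sensitivity analysis in SAP 9.7.6. These are two estimands, follow-up while non-valvular and all follow-up after index, and should be labelled so.
4. Report how many patients have a first valve code after index, by index year and exposure group. This gives the coding rate that is now unknown.

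Cost: a wording change in four places, a date filter and one censoring rule in the program, and one more run of the event-rate and Cox tables. The downside is that patients whose valve disease is recognised late contribute person-time until the code date.

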9.3.1.2 Main data available

The data available in DCIR and PMSI databases that are of importance for this study are as follows:

- Administrative data used for sociodemographic, including:
 - o Date of birth (month and year);
 - o Date of death;
 - o Sex;
 - o City, department and region of residence;
 - o CMU-C;
 - o Aid for complementary health care (ACS) for elderly patients.
- Outpatient care data, including:
 - o Health professionals visited, medical specialty for physicians, dates of visits;
 - o Dates of dispensation, dates of reimbursement, type and number of services carried out by the health professional, reimbursed costs and costs paid by the patients for the associate cares;
 - o Drugs coded according to ATC and CIP classifications;
 - o Medical and technical acts coded according to CCAM;
 - o Biological acts coded according to NABM;
 - o Medical devices coded according to LPPR;
 - o Medical transportations;
 - o Sick leaves;
- Inpatient care data, including:
 - o Type of stay coded according to DRG;
 - o Localization, type and identifier of hospitals;
 - o Dates and reasons for admissions and discharges;
 - o Main, related and significant associated diagnoses of admissions coded according to ICD-10;
 - o Drugs dispensed at hospital and costly innovative drugs administered during admissions, both coded according to ATC and the common unit of dispensation (28nité commune de dispensation, UCD) classification;
 - o Medical and biological acts performed during admissions and coded according to CCAM and NABM, respectively;
 - o Other information such as stays in resuscitation units or intensive cares.
- Medical data, including:
 - o Presence of a LTD status, start and end dates of LTD coverage and nature of LTDs coded according to ICD-10.

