9.4 Derived Variables

9.4.1 Derived Variables for the Selection of the Study Populations

First, all the variables representing the inclusion criteria will be derived for each patient (Table I).

Table I. Derived variables for the selection of the population – Inclusion criteria

Variable	Definition
Atrial fibrillation diagnosis	
Binary variable (Yes/No)
 
Equals to “Yes” if the patient meets any criterion below:
 
 – Is hospitalized at least once with any discharge diagnosis (i.e., principal, related or associated diagnosis in PMSI-MSO) of atrial fibrillation during the study (historical or inclusion) period 
ICD-10 codes: I48
 
OR
 
 – Is covered by the LTD status for atrial fibrillation at least one day during the study (historical or inclusion) period 
ICD-10 codes: I48
 
Equals to “No” in other cases

Age ≥18 years	
Binary variable (Yes / No)
 
Derived based on the date of birth attributed to the patient after cleaning the data extraction
 
Equals to “Yes” if the absolute difference between the year of index date and the year of birth is upper than or equal to 18 years
 
See also Data Management Plan in section Error! Reference source not found.
 
Equals to “No” in other cases

Second, a validated and published algorithm using a predictive model developed by Billonnet et al. (16) will be applied for the identification of AF indications in outpatients initiating OAC (Table II).

Table II. Derived variables for the selection of the population – Identification of AF outpatients initiating OAC

Variable	Definition
New users of OACs (for AF outpatients)	
Binary variable (Yes/No)
 
Equals to “Yes” if the patient receives at least one reimbursement of an OAC (VKA, apixaban, rivaroxaban or dabigatran) during the inclusion period, without use of any OAC in the 24 months prior the first date of OAC delivery

Variable	Definition
	
ATC codes: B01AA, B01AF02, B01AF01, B01AE07
 
Equals to “No” in other cases

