Unclassified patients	
Binary variable (Yes/No)
 
Equals to "Yes" if Confirmed AF = "No" and Confirmed DVT/PE = "No"
 
The algorithm will be applied on the unclassified patients. Patients with both confirmed AF and DVT/PE will be excluded.
 
Equals to "No" in other cases

Then, a logistic model included 14 independent covariables will be applied on unclassified patients to identify AF outpatients initiating OAC ([Table III](#)).

Table III. Derived variable for the selection of the population – Covariables included in the logistic model

Variable	Definition
Age	
Categorical variable (<65 years old / 65-74 / 75-79 / ≥80 years old)
 
Derived based on the date of birth attributed to the patient after cleaning the data extraction
 
Equals to:
 
 9. "<65 years old" if the absolute difference between the year of index date and the year of birth is strictly lower than 65 years old 10. "65-74" if the absolute difference between the year of index date and the year of birth is between 65 and 74 years old 11. "75-79" if the absolute difference between the year of index date and the year of birth is between 75 and 79 years old 12. "≥80 years old" if the absolute difference between the year of index date and the year of birth is upper than 80 years old 
See also Data Management Plan in section Error! Reference source not found.

Gender	Binary variable (Female / Male) Equals to the value attributed to the patient after cleaning the data extraction See Data Management Plan in section Error! Reference source not found.
Cardiologist prescriber	Binary variable (Yes / No) Equals to "Yes" if the prescriber of the initiation of the OAC is a cardiologist Code CNAM repository (variable PSE_SPE_COD): 03 Equals to "No" in other cases
Initiation of beta-blockers	Binary variable (Yes / No) Equals to "Yes" if the patient has reimbursements for at least one dispensation at pharmacy of any beta-blockers during the 6 weeks preceding the first date of OAC delivery and with no filled prescription for the medication during the previous 180 days ATC codes: C07xxxx Equals to "No" in other cases
Use of beta-blockers	Binary variable (Yes / No) Equals to "Yes" if the patient has reimbursements for at least one dispensation at pharmacy of any beta-blockers during the 6 weeks preceding the first date of OAC delivery ATC codes: C07xxxx Equals to "No" in other cases

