Age ≥ 80 years old	
Binary variable (<80 years old / ≥ 80 years old)
 
Derived based on the date of birth attributed to the patient after cleaning the data extraction
 
Equals to:
 
 13. “<80 years old” if the absolute difference between the year of index date and the year of birth is strictly lower than 80 years old 14. “≥ 80 years old” if the absolute difference between the year of index date and the year of birth is upper than 80 years old 
See also Data Management Plan in section Error! Reference source not found.

History of coronary arterial disease (CAD)	
Binary variable (Yes / No)
 
Equals to “Yes” if the patient meets any criterion below on or in the 2 years prior to the index date:
 
 15. Is hospitalized with any diagnosis (i.e., main, related or associated diagnosis) of coronary arterial disease 
ICD-10 codes: I21.x, I22.x, I24.x, I25.x
 
OR
 
 – Is covered by the LTD status for coronary arterial disease at least one day 
ICD-10 codes: I21.x, I22.x, I24.x, I25.x
 
Equals to “No” in other cases

Claims-based Frailty Index (CFI) (for frail patients’ derivation)	
Continuous variable (between 0 and 1)
 
Claims-based frailty index (CFI) estimates a deficit-accumulation frailty index from a clinical assessment using International Classification of Diseases (ICD) diagnosis codes, Current Procedural Terminology (CPT) codes, and Healthcare Common Procedure Coding System (HCPCS) codes in the prior 2 years in administrative claims data.
 
See more details on calculation of CFI in Appendix 22

Frail patients	
Binary variable (Yes / No)
 
Equals to “Yes” if the Claims based Frailty Index (CFI) is upper or equal to 0.20
 
See Table I variable Claims based Frailty Index (CFI)

Active cancer	Binary variable (Yes / No)

Equals to “Yes” if the patient meets any criterion below in the 2 years before index date:
 
16. Is hospitalized with any discharge diagnosis (i.e., main, related or associated diagnosis) of active cancer
 
ICD-10 codes: C00.x to C80.x, D00.x to D09.x, D37.x to D48.x, Z51.0, Z51.1
 
OR
 
 – Is covered by the LTD status for active cancer at least one day 
ICD-10 codes: C00.x to C80.x, D00.x to D09.x, D37.x to D48.x, Z51.0, Z51.1
 
Equals to “No” in other cases
	

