	
 - Has reimbursements for 2 dispensations at pharmacy of any antihypertensive drug, of which at least one in a package containing >80 pills 
ATC codes: C02AB02, C02AC01, C02AC02, C02AC05, C02AC06, C02CA01, C02CA02, C02CA06, C02DC01, C02LA01, C03AA01, C03AA03, C03BA04, C03BA10, C03BA11, C03BX03, C03CA01, C03CA02, C03CA03, C03DA01, C03DA02, C03DA04, C03DB01, C03EA, C03EA01, C03EA04, C03EB01, C07AA02, C07AA03, C07AA05, C07AA06, C07AA07, C07AA12, C07AA15, C07AA16, C07AA23, C07AB02, C07AB03, C07AB04, C07AB05, C07AB07, C07AB08, C07AB12, C07AG01, C07AG02, C07BA02, C07BB02, C07BB03, C07BB07, C07BB12, C07CA03, C07DA06, C07FB02, C07FB03, C08CA01, C08CA02, C08CA03, C08CA04, C08CA05, C08CA06, C08CA08, C08CA09, C08CA11, C08CA13, C08CX01, C08DA01, C08DB01, C08EA02, C09AA01, C09AA02, C09AA03, C09AA04, C09AA05, C09AA06, C09AA07, C09AA08, C09AA09, C09AA10, C09AA13, C09AA15, C09AA16, C09BA01, C09BA02, C09BA03, C09BA04, C09BA05, C09BA06, C09BA07, C09BA09, C09BA15, C09BB02, C09BB04, C09BB10, C09CA01, C09CA02, C09CA03, C09CA04, C09CA06, C09CA07, C09CA08, C09DA01, C09DA02, C09DA03, C09DA04, C09DA06, C09DA07, C09DA08, C09DB01, C09DB02, C09DB04, C09XA02, C09XA52, C10BX03

Age groups (for Modified CHAD ₂ DS ₂ VASC score strata derivation)	Categorical variable (<65, 65-74, ≥75 years old) See Table III
Diabetes history (for Modified CHAD ₂ DS ₂ VASC score strata derivation)	Binary variable (Yes / No) Derived based on (24) Equals to "Yes" if the patient meets any criterion below on or in the 2 years prior to the index date:

- Is hospitalized with a main or related diagnosis of diabetes
ICD-10 codes : E10.x, E11.x, E12.x, E13.x, E14.x

OR

- Is hospitalized with the two criteria:
 - o A main or related diagnosis of complication of diabetes
ICD-10 codes: G59.0, G63.2, G73.0, G99.0, H28.0, H36.0, I79.2, L97, M14.2, M14.6, N08.3

AND

- o A significant associated diagnosis of diabetes
ICD-10 codes : E10.x, E11.x, E12.x, E13.x, E14.x

OR

- Is covered by the LTD status for diabetes at least one day
ICD-10 codes : E10.x, E11.x, E12.x, E13.x, E14.x

OR

- Has reimbursements for at least 3 dispensations at pharmacy of any glucose-lowering drug
ATC codes: A10Axx, A10Bxx excepted for A10BX06

OR

- Has reimbursements for 2 dispensations at pharmacy of any glucose-lowering drug, of which at least one in a package containing >80 pills
ATC codes: A10Axx, A10Bxx excepted A10BX06

Equals to "No" in other cases

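### SAP Tables III and V leave a patient whose year difference is exactly 80 in no age group, and age is a difference of calendar years although month of birth is available

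*SAP*

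**What the plan says.** SAP 9.4.1 derives age in Tables I, III and V from the year of the index date minus the year of birth.

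- **Table V, elderly subgroup.** The variable is declared binary (<80 / ≥80). The lower category applies "if the absolute difference between the year of index date and the year of birth is strictly lower than 80 years old". The upper one applies "if the absolute difference between the year of index date and the year of birth is upper than 80 years old".
- **Table III, four bands (<65, 65-74, 75-79, ≥80).** The third band applies "if the absolute difference between the year of index date and the year of birth is between 75 and 79 years old". The fourth repeats the wording of the upper category in Table V.
- **Table I, adults.** The age criterion is inclusive: the absolute difference between "the year of index date and the year of birth is upper than or equal to 18 years". The frailty cut-off in Table V is also worded inclusively.
- **Available data.** SAP 9.3.1.2 lists month as well as year of birth.

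These definitions are used widely. Age ≥80 is a subgroup of the primary objective (SAP 8.1, 9.2.3.4). The Table III bands are the ones used to age-standardise the unexposed primary rates (SAP 9.7.3.1, footnote to Table A2). Table III age is also one of the 14 covariables of the AF-identification model (SAP 9.2.3.1). The CHA2DS2-VASc age item in Table VI reads "Categorical variable (<65, 65-74, ≥75 years old) See Table III".

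**The concern.** There are two separate faults.

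The first is a gap. Label and rule disagree at 80, and the SAP uses inclusive wording elsewhere when it means ≥. Read as written, a difference of 80 belongs to no elderly category, no standardisation band and no level of the algorithm's age predictor. SAP 9.6 says derived variables are programmed from the instructions in the signed-off SAP, so the written rule matters.

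The second is the age measure itself. Subtracting calendar years ignores whether the birthday has passed by the index date. Patients in their last year below 65 or 75 can be given the higher CHA2DS2-VASc age points and, at 75, be moved from the moderate to the high stratum. The high stratum defines the restricted Cox population in SAP 9.7.4.2.

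**Working it through.** The plan gives no figure for this point, so there is nothing to reproduce. The gap itself needs no assumption. Its size does.

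**1. Logic of the written intervals** (D = index year − birth year)

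| D | Table III | Table V |
|---|---|---|
| 79 | 75-79 | <80 |
| 80 | none | none |
| 81 | ≥80 | ≥80 |

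**2. Assumed ages.** The only age figure in the documents is that two-thirds of AF patients are 75 or older (SAP 7.1). Two families fit it:

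- (a) two-thirds uniform from 75 to an upper limit of 90, 95 or 100, and one-third uniform from 45 or 55 to 75;
- (b) normal distributions with two-thirds at or above 75 and SD 9 to 11.6.

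**3. Share with D = 80.**

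- Family (a): (2/3) / (upper limit − 75), which is (2/3)/15 = 4.4%, (2/3)/20 = 3.3% and (2/3)/25 = 2.7%.
- Family (b), by simulation: 3.4–4.4%.
- For scale, 225,747 new OAC users per year (SAP 9.5) × 4 years = 902,988. At 2.7–4.4% that is about 24,000–40,000 patients, if the same share applies to them.

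**4. How many of these are truly 80.** About half of those with D = 80 have not had their birthday and are 79. The loss among patients truly aged ≥80, family (a), is:

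| Upper limit | Half of the gap | True share ≥80 | Lost |
|---|---|---|---|
| 90 | 2.22% | (2/3)(10/15) = 44.4% | 5.0% |
| 95 | 1.67% | (2/3)(15/20) = 50.0% | 3.3% |
| 100 | 1.33% | (2/3)(20/25) = 53.3% | 2.5% |

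Family (b) gives 3.4–4.9%.

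**5. One-year error.**

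- With birthday and index day independent and uniform, the share with the birthday still to come is Σ(365 − d)/365² = 49.9%.
- Prevalent patients are included on 1 January 2016 (SAP 9.2.1.2). For those indexed on that day the share is 364/365 = 99.7%.

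**6. Who changes group at 65 and 75.** Half of the patients in the last year below the cut-point.

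- Family (a): ½ × (1/3)/30 = 0.56%, or ½ × (1/3)/20 = 0.83%, at each cut-point; together 1.1–1.7%.
- Family (b): 0.6–0.7% at 65 and 1.6–2.0% at 75; together about 2.3–2.6%.

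**7. At 80.** D above 80 implies a completed age of at least 80, so as written nobody under 80 enters the elderly group. If the rule were changed to D ≥ 80 with calendar-year subtraction kept, family (a) puts 79-year-olds at 2.4–4.8% of that group.

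**8. Effect on the elderly rate.** Let a share l be lost, with an event rate r times that of the full group. The relative change is (1 − l·r)/(1 − l) − 1. For l = 2.5% and r = 0.8 this is +0.5%. For l = 5% and r = 0.5 it is +2.6%. The range for r is an assumption.

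**The case against.** The strongest reply is that this is a wording slip with little consequence. The label ≥80 appears consistently in the objectives, subpopulations and table shells, and a binary variable has no room for a third state. A second statistician checks the programs, the rate in the elderly group moves by a few per cent at most, and calendar-year subtraction applies equally to exposed and unexposed patients. Much of this stands: the intent is clear, the effect is modest, and no comparative bias has been shown. It does not remove the point. A program that follows the written rule leaves the gap open. The tables' cross-reference to the data management plan does not resolve, and SAP 9.6 contains no age rule.

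A reader might also infer more than the documents support:

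- *That half of all patients are misclassified.* Half carry a one-year error, but only those just below a cut-point change group.
- *That 79-year-olds are in the elderly group.* As written they cannot be (step 7).
- *That the elderly group loses 7–9%.* That counts the whole gap against the group, although half of those in the gap are 79.
- *That patients at 80 get no CHA2DS2-VASc age points.* The score has its own ≥75 category, which Table III lacks. The reference to Table III most naturally concerns how age is computed, and a difference of 80 then scores 2 points. The ACCI age points are inclusive at 80. The HAS-BLED age item has no stated derivation.

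Finally, completed age from month and year is not exact, and changing the age predictor could depart from the published algorithm, whose age definition the documents do not show. Both points are fair and are reflected in the fix.

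**Conclusion.** The gap at a year difference of 80 is certain from the text of Tables III and V. Its size rests on age distributions matched only to the two-thirds figure: about 3–4% of patients have no category, and roughly 2.5–5% of those truly aged 80 or over are lost from the elderly subgroup and the top standardisation band. The one-year overstatement is equally certain in kind. It affects about half of incident patients and changes the group of roughly 1–3% at 65 and 75 together. The elderly rate would rise by an estimated 0.5–2.6% in relative terms. This should be corrected because a primary subgroup and the primary standardisation depend on it and the correction is cheap. It does not threaten the study's conclusions.

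**What to change.** 1. In Tables III and V, define the top category as age ≥80.
2. Compute completed age at index once, from birth month and year and the index date. State a convention for patients whose birth month equals the index month (about 1/12 = 8.3%), who otherwise stay uncertain by one year.
3. Use this variable for the elderly subgroup, the standardisation bands and the age items of the scores, and give the HAS-BLED age item an explicit derivation.
4. For the AF-algorithm predictor, close the gap at 80 but keep the age definition of the published algorithm, and state it.

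Item 1 alone closes the gap but, with calendar-year subtraction kept, admits 79-year-olds, so items 1 and 2 belong together. The cost is a few lines in the SAP and one derivation in the program. No new data are needed.
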